11.3.2 Analysis of Clinical Laboratory parameters

Laboratory results during open-label extension will be summarized by OLE treatment groups. For these summary tables, results will be reported using visit windows as defined in Appendix 14.2. Shift tables from baseline to each post-baseline OLE visit will be prepared for hematology and chemistry laboratory assessments based on the categories of Low, Normal, and High (for numerical results) or Abnormal and Normal (for categorical results). Baseline measurement is defined as the last available measurement prior to dosing in double-blind.

Laboratory results during OLE will be listed by subject.

11.3.3 Analysis of Electrocardiograms

All ECG results will be listed on a by-subject basis. ECG parameters consist of heart rate (bpm), PR interval (msec), RR interval (msec), QRS-complex (msec), uncorrected QT interval (msec), and QTcF interval (msec). Individual ECG values (parameters) will be listed by subject and visit. Baseline measurement is defined as the last available measurement prior to dosing in double-blind period.

For summary tables, the following rules will be applied to derive a single value corresponding for this visit:

- For all numerical values, the average of the 3 measurements will be computed
- For qualitative values (normal / abnormal):

SAP-OLE Version Final_15May2021 Page 30 of 43

- If 2 or more results are "abnormal", visit 3 derived results will be "abnormal" (this rule applies for subjects with 3 or 2 measurements)
- Otherwise, visit 3 derived results will be "normal".

For subjects with only one measurement collected at Visit 1 (DB baseline),

the collected value will be used as baseline value for summary results.

For the OLE-SE analysis population the following summary tables will be generated for the ECG data:

- Summary statistics (n, mean, standard deviation, median, minimum, and maximum) of the baseline value, the value at each scheduled postbaseline evaluation, and the corresponding change from baseline for each continuous ECG parameter,
- Count and percentage of subjects with QTcF absolute value > 450 msec, >480 msec, >500 msec, <360 msec, <340 msec, <320 msec, and <300 msec at each scheduled post-baseline evaluation,
- Count and percentage of subjects with a mean change from baseline in QTcF intervals >30 msec, >60 msec >90 msec, <30 msec, <60 msec, and <90 msec at each scheduled post-baseline evaluation,
- Count and percentage of subjects with absolute heart rate > 100 bpm at each scheduled post-baseline evaluation,
- Count and percentage of subjects with heart rate change from baseline >10 bpm, >20 bpm, and >30 bpm at each scheduled post-baseline evaluation,

For these summary tables, results will be reported using visit windows as defined in Appendix 14.1.

ECG results during OLE will be listed by subject.

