4.4.3 *Safety Pharmacology and Toxicity Studies*

Details of the preclinical safety and toxicity studies of YKP3089 can be found in the Investigator's Brochure. The most common AEs in preclinical studies of YKP3089 involved the central nervous system (CNS). The incidence and severity of these signs increased with

increasing dose, and the signs resolved during the recovery periods. In mice and rats, the median neurotoxic dose of YKP3089 was calculated to be between 50 and 350 mg/kg, a dose greater than that required to elicit antiepileptic effects (ie, 3 to 30 mg/kg).

In a special neurotoxicity safety pharmacology study in cynomolgus monkeys, no evidence of drug-induced epileptic convulsions was observed at 30, 40, or 60 mg/kg/day administered for 4 days. Severe toxicity was noted at 40 and 60 mg/kg/day requiring euthanasia of 1 animal and halting of dosing for 3 others before the end of the scheduled 4 days of administration. At 60 mg/kg/day, myoclonus and/or intention tremors were noted in 2 of 6 animals.

YKP3089 had no effect on cardiac (ECG) or circulatory function in monkeys, as measured by telemetry. Nor was there evidence of cardiotoxicity in studies of rats or monkeys. YKP3089 at doses up to 30 mg/kg had no effect on pulmonary function or cause bronchoconstriction.

Reproductive toxicity studies showed adverse effects on reproductive performance when the dosage of YKP3089 was high enough to induce maternal toxicity, as evidenced by decreased food consumption and decreased body weight. However, there was no evidence of teratogenicity.

The results of standard genotoxicity studies of YKP3089 were negative. No tests of carcinogenicity have been conducted.

4.4.4 *Clinical Safety*

Approximately 400 human subjects have been exposed to YKP3089 in 15 completed (13 Phase 1, 1 proof-of-concept) and 1 Phase 2a).

In a multiple ascending dose study in healthy volunteers, when doses of 250 to 300 mg once daily were given from Day 1, somnolence, dizziness, and decreases in mean systolic blood pressure have been seen, but no serious AEs have been reported. Horizontal nystagmus, ataxia, and gait disturbance have also been observed in normal volunteers receiving 250 and 300 mg once daily. These reactions resolved after YKP3089 was discontinued at the end of the study. At 300 mg once daily, a mean shortening of the QT_{CF} interval of 10 to 15 msec was observed.

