17. Current or recent (within the past year) use of vigabatrin. Subjects with a prior history of treatment with vigabatrin must have documentation showing no evidence of a vigabatrin associated clinically significant abnormality in a visual perimetry test.
18. History of status epilepticus within 3 months of Visit 1
19. History of 1 serious drug-induced hypersensitivity reaction (including but not limited to Stevens Johnson syndrome, toxic epidermal necrolysis, drug reaction with eosinophilia and systemic symptoms) or any drug-related rash requiring hospitalization
20. History of AED-associated rash that involved conjunctiva or mucosae or more than one maculopapular rash that required discontinuation
21. Creatinine clearance less than 50 mL/min, as calculated by the Cockcroft-Gault equation
22. Absolute neutrophil count less than 1500/ μ L
23. Clinical or ECG evidence of serious cardiac disease, including ischemic heart disease, uncontrolled heart failure, and major arrhythmias, or relevant replicated changes in QT intervals (QTcF less than 340 msec or greater than 450 msec in males and greater than 470 msec in females)

24. Platelet counts lower than 80,000/ μ L in subjects treated with VPA
25. A "yes" answer to Question 1 or 2 of the C-SSRS (Baseline/Screening version) Ideation Section in the past 6 months or a "yes" answer to any of the Suicidal Behavior Questions in the past 2 years.
26. More than 1 lifetime suicide attempt
27. Participation in any other trials involving an investigational product or device within 30 days of screening (or longer, as required by local regulations)
28. Current use of any of the following medications: clopidogrel, fluvoxamine, amitriptyline, clomipramine, bupropion, methadone, ifosfamide, cyclophosphamide, efavirenz, or natural progesterone (within 1 month of Visit 1)
29. History of positive antibody/antigen test for hepatitis B, hepatitis C, or HIV
30. Presence of congenital short QT syndrome
31. A history of any previous exposure to YKP3089

Any potential exception to exclusion criteria allowing *de minimis* (clinically trivial and meaningless) variations must be approved by the medical monitor.

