 - a. The blinded 2-week crossover period (for subjects participating in the open-label extension), during which all subjects will be converted to a target dose of 300 mg once daily, of open-label YKP3089. During the first week of the conversion period, the investigator can increase or decrease the open-label dosage by 50-100 mg if clinically indicated. During the second week of the conversion period, the investigator can decrease the open-label dosage by 50-200 mg or increase the open label dosage by a maximum of 100 mg if clinically indicated.

- b. The open-label extension period: Refer to section 6.1.4.2 of the protocol for details on the open label extension.
- c. The taper period of 3 weeks with a final follow-up visit 2 weeks after the last dose of study drug. Refer to section 6.1.4.3 of the protocol for details and the table for taper period.

Figure 1 Study Flowchart

Study assessment chart for double-blind period is included in DB SAP. OLE SAP includes details for study assessment chart for OLE only.

Table 1 Study Assessment Flow Chart for Open-Label Extension Phase

Visit windows of ± 3 days allowed for Visits 9 and Visit 17 (end of study follow-up visit)				Treatme	nt		End of Study Follow-up		
Visit windows of ± 2 days allowed for Visits 11 and 12. Visit windows of ± 7 days allowed for all other open-label visits	Visit 9 First Day of	Visit 11	Visit 12	Visit 13	Visit 14		Visit 16 or Terminati on Visit	Post 1 year	Visit 17
Assessment	Day 127ª	Day 141	Day 155	Day 239	Day 323	Day 407	Day 491	Every 3 months ^b	14 days after the last dose
Inclusion/exclusion ^c	Х								
Vital signs ^d	Χ	Х	Х	Х	Х	Х	Х	Х	Х
Weight	Χ			X		Χ	Х	Xe	Х
Full physical examination	Χ						Х	X ^f	
Full neurologic examination	Х						Х		Х
Brief neurologic exam		X		X		Χ		Xe	
C-SSRS ^g	Χ	X	X	X	X	X	Х	Χ	Х
ECG ^h	Χ		X				X	X ^f	

Serum pregnancy test ⁱ									Х
Urine pregnancy test ⁱ	Х		Х		Х		Х	Xe	
Laboratory safety assessment ^j	Х		Х		Х		Х	Xe	Х
Urinalysis	Х				Х		Х	X ^f	Х
Concomitant medication	Х	Х	Х	Х	Х	Х	Х	Х	Х
Dispense/review/ collect seizure diary	Х	Х	Х	Х	Х	Х	Х	Х	
Drug accountability	Х	Х	Х	Х	Х	Х	Х	Х	Х
Dispense study drug	Χ	Х	Х	Х	Х	Х	Х	Х	
Adverse events	Х	Х	Х	Х	Х	Х	Х	Х	Х

C-SSRS = Columbia Suicide Severity Rating Scale; ECG = electrocardiogram; AED = antiepileptic drug.

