- a. Visit 9 is the same as Visit 9 at the end of double-blind maintenance phase, except that study drug for 2-week blinded crossover period to open-label extension will be dispensed to subjects who will participate in the open-label extension.
- b. After 12 months of participation in the open-label extension phase, subjects will be re-evaluated. Those who are benefiting from treatment with YKP3089 may continue use of the drug at the discretion of the investigator, until development is stopped by SK Life Science Inc, or the product is approved for marketing, or anytime at the discretion of SK Life Science Inc.
- c. Subject should continue to meet the inclusion and exclusion criteria except for seizure frequency.
- d. Vital signs include blood pressure and heart rate (supine for 5 minutes followed by standing for 3 minutes). Respiration rate and oral temperature in the supine position.
- e. Every 6 months after Visit 16.
- f. Every 12 months after Visit 16.
- g. Administer the Since Last Visit version of the C-SSRS.
- h. 12-lead ECG. Additional ECGs should be performed at any other time if clinically indicated.
- i. If pregnancy is suspected at any time during the study, an interim test may be performed.
- j. Laboratory assessment: Safety assessment includes blood chemistry and hematology.

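### The open-label QTcF counts below 360 msec, and above 450 msec in women, mix values already present at entry with new ones, because no baseline condition is set

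*SAP*

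**What the plan says.** SAP 11.3.3 lists the ECG tables for the OLE safety population. One is a "Count and percentage of subjects with QTcF absolute value > 450 msec, >480 msec, >500 msec, <360 msec", continuing with "<340 msec, <320 msec, and <300 msec at each scheduled post-baseline evaluation". Men and women share the same cut-offs, and the baseline value plays no part in the count. The section sets the baseline before any study drug: "Baseline measurement is defined as the last available measurement prior to dosing in double-blind period".

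Two other tables in the section do use baseline. One gives summary statistics of the baseline value, each visit value and the change. The other counts subjects by "mean change from baseline in QTcF intervals >30 msec, >60 msec >90 msec, <30 msec, <60 msec, and <90 msec". SAP 8.4 also summarises baseline ECG, and all ECG results are listed by subject.

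Exclusion 23 (Protocol 7.4) rules out "QTcF less than 340 msec or greater than 450 msec in males and greater than 470 msec in females". SAP section 6 (Table 1, footnote c) applies the criteria again at OLE entry: "Subject should continue to meet the inclusion and exclusion criteria except for seizure frequency".

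On the expected direction, Protocol 4.4.4 reports that in healthy volunteers at 300 mg once daily a mean shortening of the QTcF "interval of 10 to 15 msec was observed". In the extension, "all subjects will be converted to a target dose of 300 mg once daily, of open-label YKP3089".

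**The concern.** An absolute QTcF count is read as a sign of what happens on drug. That reading is weakened when a cut-off lies inside the range the protocol accepts at entry, because the count then adds new crossings to values that were there before the first dose.

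It matters more here for two reasons. The extension has no control group, so the subject's own pre-treatment value is the main reference. And <360 msec is the first cut-off in the direction of the shortening reported at 300 mg once daily, which is also the OLE target dose.

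The SAP already handles laboratory data in the better way: SAP 11.3.2 plans shift tables from baseline to each OLE visit for hematology and chemistry. QTcF has no equivalent. At stake is how clearly a descriptive safety table can be read. No efficacy result is touched.

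**Working it through.** The plan states no figure to reproduce here. The check has a structural part, which rests on the documents alone, and an illustration of size, which rests on assumptions.

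**1. Cut-offs against the entry range** (SAP 11.3.3; Protocol 7.4, exclusion 23)

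| Cut-off (msec) | Men, entry 340-450 | Women, entry 340-470 |
|---|---|---|
| <360 | inside | inside |
| <340, <320, <300 | outside | outside |
| >450 | outside | inside |
| >480, >500 | outside | outside |

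The overlap is 340 to <360 msec in both sexes and >450 to 470 msec in women. The limits are not absolute: exclusion 23 speaks of replicated changes, and the protocol allows trivial exceptions.

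**2. What the other planned outputs show**

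- Mean, SD, median, minimum and maximum at baseline show whether an extreme value exists, not how many subjects have one.
- Counts by change from baseline are a separate table. A subject moving from 375 to 355 msec and one staying at 355 msec both enter the <360 count, and neither has a change of 30 msec. The lower change categories also appear without a minus sign in the text available; read literally, they would include subjects with no change.
- Appendix 14.1 has a Visit 9 window. For the former placebo group this is close to an off-drug rate. The other three groups are already on YKP3089 at that visit.
- The by-subject listings would allow new crossings to be worked out by hand.

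**3. Illustration of size**

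Assumptions (none from the documents): normal QTcF; male mean m = 390-405 msec, women 10 higher; between-subject SD b = 15-20; within-subject SD w = 10-12; half women; entry limits applied to the baseline reading.

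Total SD s = √(b² + w²); correlation of two readings r = b²/s²; upper entry limit U = 450 (men) or 470 (women).

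Share of eligible subjects <360 at baseline = [Φ((360−m)/s) − Φ((340−m)/s)] / [Φ((U−m)/s) − Φ((340−m)/s)].

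Given baseline x, a later reading with drug shift d has mean m + r(x−m) + d and SD s√(1−r²). The pre-existing share is P(baseline <360 and later <360) / P(later <360).

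Example with m = 400/410, b = 18, w = 10, so s = √424 = 20.6:

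- Men <360: (0.0260 − 0.0018)/(0.9924 − 0.0018) = 2.4%.
- Women <360: (0.0076 − 0.0003)/(0.9982 − 0.0003) = 0.7%.
- Average: 1.6%.
- Women >450: (0.0260 − 0.0018)/(0.9982 − 0.0003) = 2.4%.

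Results across the assumed range, with d = −12.5 msec (the middle of 10 to 15):

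| Male mean / b / w | <360 at baseline | <360 on treatment | Pre-existing share of <360 | Women >450 at baseline |
|---|---|---|---|---|
| 390/15/10 | 2.9% | 11.4% | 17.8% | 0.3% |
| 390/20/10 | 5.6% | 15.7% | 28.4% | 1.2% |
| 390/20/12 | 6.2% | 16.6% | 26.6% | 1.5% |
| 400/18/10 | 1.6% | 6.2% | 18.0% | 2.4% |
| 405/15/10 | 0.4% | 2.3% | 9.0% | 2.5% |
| 405/15/12 | 0.6% | 3.0% | 8.5% | 3.2% |
| 405/20/12 | 1.7% | 5.8% | 17.9% | 5.8% |

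A simpler model (one normal distribution, mean 395-425, SD 15-20, cut to the entry range) gives about 0-3.7% of eligible subjects <360 and about 0-9.5% of eligible women >450.

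In people, for the 400/18/10 row: if all 400 randomised subjects entered the extension (an upper bound), 6.2% × 400 ≈ 25 would be <360 at a visit, of whom 0.18 × 25 ≈ 4 to 5 were already there.

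**The case against.** The strongest reply is that baseline is not ignored. Change from baseline is summarised and counted in the same section, baseline extremes are shown, Visit 9 in the former placebo group gives a background rate at the same cut-offs, and the extension is descriptive only (SAP 11.1). The SAP does not call these values treatment-emergent. Table templates are in a separate document (SAP section 4), so a baseline column cannot be ruled out. All of this stands, and it keeps the point small. It does not answer which subjects newly crossed a cut-off.

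Three stronger readings are tempting and are not supported.

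- A reader might infer that a subject eligible at 350 msec, or a woman eligible at 460 msec, is counted at every visit. Readings vary within a subject. In the 400/18/10 example with no drug effect, only about 35% of those <360 at baseline are <360 at a given later visit, and about 37% of women >450 are again >450.
- A reader might infer a false prolongation signal in women. In the same example with a 12.5 msec shortening, women >450 fall from 2.4% at baseline to about 0.46% on treatment, so the count goes down.
- A reader might conclude that >450 should become >470 for women. Exclusion 23 sets an eligibility limit, which need not be a reporting threshold, and conditioning on baseline makes the change unnecessary.

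Conditioning has its own limit. With no drug effect in that example, about 65% of the <360 count would still be new crossings, from within-subject variation alone.

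**Conclusion.** The point holds as a minor reporting weakness. It is certain from the documents that the <360 count in both sexes and the >450 count in women can include values accepted at entry, that the other cut-offs are free of this overlap, and that no table described in the SAP separates new from pre-existing crossings.

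The size is not known from the documents. Under the assumptions listed, about 0.4-6% of eligible subjects are <360 msec and about 0.3-6% of eligible women are >450 msec at baseline; with a 12.5 msec shortening, about 9-28% of the <360 count is pre-existing. A clear rise, such as 1.6% to 6.2% in the example, would still be visible. The shortening figure comes from healthy volunteers. The separate double-blind SAP was not available and may hold placebo-controlled ECG comparisons.

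**What to change.** In SAP 11.3.3 keep the absolute counts and add:

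- a baseline column showing how many subjects are beyond each cut-off before double-blind dosing;
- for each cut-off, the count and percentage among subjects not beyond it at baseline, or a baseline-by-post-baseline shift table like those in SAP 11.3.2;
- the >450 msec row by sex.

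The sign of the lower change-from-baseline categories should be confirmed at the same time.

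The cost is SAP wording and a few columns; the baseline is already defined and no new data are needed. The downsides are that denominators differ slightly between cut-offs, and that some new crossings will still reflect within-subject variation rather than drug, which a footnote should say.

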Safety during the double-blind phase will be assessed by the nature, frequency, and severity of treatment-emergent spontaneously reported AEs, dropouts due to AEs, overall dropout rates, and changes from baseline in vital signs, physical and neurologic exams, clinical laboratory evaluations, 12-lead ECGs, and Columbia-Suicide Severity Rating Scale (C-SSRS) in YKP3089-treated subjects compared to placebo-treated subjects.

Any patient who reports a rash by telephone or is observed to have a rash should be carefully evaluated for a drug hypersensitivity syndrome; the evaluation should include hematology and chemistry blood tests. If a subject reports a rash by telephone, an unscheduled visit should be performed promptly.

Adverse Events

Adverse events (AEs) will be reported by the subject (or, when appropriate, by a caregiver, surrogate, or the subject's legally acceptable representative) for the duration of the study. AEs will be followed by the investigator for a length of time as determined by the sponsor. Specific details on AE reporting are provided in Section 11.

Clinical Laboratory Tests

- Hematology: hemoglobin, hematocrit, white blood count with differential, RBC count, platelet count, and calculated indices

- Serum chemistry: blood urea nitrogen (BUN), calcium, chloride, creatinine, glucose, total bilirubin, direct bilirubin, alkaline phosphatase, aspartate transaminase (AST), alanine aminotransferase (ALT), albumin, sodium, potassium, phosphorus, and glucose. Serum creatinine will be used to calculate the creatinine clearance.
- Urinalysis: pH, specific gravity, protein, glucose, ketone, bilirubin, blood, nitrite, urobilinogen, and microscopic examination
- Pregnancy Tests – All females of child-bearing potential will undergo a serum pregnancy test for β -hCG (β -human chorionic gonadotropin) at Visits 1 and 10 and urine pregnancy tests performed at the clinical site at Visit 3 & 9 which will be confirmed by a serum pregnancy test if positive.

Electrocardiogram

Triplicate (to be performed 3 times with a minimum of 2 minutes between each recording) and routine 12-lead ECGs will be performed periodically during the study.

Vital Signs

Blood pressure and heart rate will be measured after the subject has been supine for 5 minutes and again after the subject has been standing for 3 minutes. Respiratory rate and oral temperature will be measured with the subject supine.

Physical and Neurologic Examinations

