14 APPENDIX 2: VISIT WINDOWS

14.1 ECG

The following visit windows will be applied for reporting **ECG** results open-label extension results:

Analysis Timepoint	C017 OLE	
	Target Study Day [1]	Window [2]
		Study Days
Baseline	1	<= 1
Start of OLE [3] – Visit 9	127	>= 113 to <= 141
Visit 12	155	>=142 to <= 323
Visit 16	491	>=324 to <=659
Visit 20	827	>=660 to <= 995
Visit 24	1163	>=996 to <=1306
Visit 28	1499	>=1307 to <=1642
Visit 32	1835	>=1643 to <= 2003
Visit 36	2171	>= 2004 to <=2339
Visit 40	2507	>= 2340 to <= 2675
Visit 44 [4]	2843	>=2676

OLE=Open-label Extension

^[1] Relative to the date of the first dose of study drug. For example, Day 1 = the date of the first dose of study drug.

^[2] The study days evaluated for windows of visits during treatment period are on or prior to the last dose day.

^[3] This window should include the study day when the first dose of OLE study medication was given.

^[4] Expected timepoint C017 OLE.

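### The open-label SAP tabulates QTcF, heart-rate and laboratory abnormalities only visit by visit, with no count of subjects ever abnormal and no rule for unscheduled or multiple records in a window

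*SAP*

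**What the plan says.** **ECG.** SAP 11.3.3 lists the planned ECG tables. QTcF limits are counted as "<340 msec, <320 msec, and <300 msec at each scheduled post-baseline evaluation". Heart rate follows the same pattern: "Count and percentage of subjects with absolute heart rate > 100 bpm at each scheduled post-baseline evaluation". The changes from baseline in QTcF and heart rate are also counted per scheduled evaluation. The section then adds: "For these summary tables, results will be reported using visit windows as defined in Appendix 14.1".

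**Laboratory.** SAP 11.3.2 states: "Shift tables from baseline to each post-baseline OLE visit will be prepared for hematology and chemistry laboratory assessments". It also says: "For these summary tables, results will be reported using visit windows as defined in Appendix 14.2". It does not use the word scheduled.

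**Windows.** SAP Appendix 14.1 and 14.2 define day ranges for each visit, with this limit: "The study days evaluated for windows of visits during treatment period are on or prior to the last dose day".

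**Unscheduled tests are expected.** SAP Table 1, footnote h (Section 6): "Additional ECGs should be performed at any other time if clinically indicated". Protocol 9.5 allows laboratory tests whenever the investigator judges them necessary. For a patient with a rash, Protocol 6.3 says "the evaluation should include hematology and chemistry blood tests", and a rash reported by telephone should lead to a prompt unscheduled visit.

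**Listings.** All ECG results and all OLE laboratory results are listed by subject.

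**The concern.** In an extension that runs for years, the natural safety question is how many subjects ever crossed a limit. Two statements in the protocol make that question relevant to this drug. Protocol 4.4.4 reports a mean QTcF shortening of 10 to 15 msec at 300 mg once daily, and 300 mg/day is the OLE target dose. Protocol 4.6 describes a case consistent with DRESS, with eosinophilia and hepatic enzyme abnormalities, judged probably related.

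The planned tables answer a different question: how many subjects were abnormal at Visit 12, at Visit 16, and so on. The rows cannot be added, because the same subject may appear in several of them.

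Scheduled ECGs are also sparse, at yearly intervals after Visit 16 (SAP 10.3). An ECG taken between visits for symptoms may be the only record of an excursion, so how such a record enters the tables needs to be stated.

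**Working it through.** The plan gives no figure to reproduce here. The check has two parts: what the windows do with off-schedule records, and what by-visit counts imply about subjects ever abnormal.

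**1. Windows (SAP Appendix 14.1 and 14.2)**

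- ECG: ten OLE windows from day 113, nine of them after Visit 9 (Visits 12, 16, 20, 24, 28, 32, 36, 40, 44). Each starts the day after the previous one ends, and the last is open-ended, so there is no gap.
- ECG widths (end − start + 1): Visit 12, 323 − 142 + 1 = 182 days. Visits 16, 20, 28, 36 and 40 are 336 days each (Visit 16: 659 − 324 + 1). Visit 24, 1306 − 996 + 1 = 311. Visit 32, 2003 − 1643 + 1 = 361.
- Laboratory: 18 OLE windows, 17 after Visit 9, most of them 168 days wide. The only gap is days 2757 to 2759 (Visit 42 ends at 2756, Visit 44 starts at 2760).

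An unscheduled on-treatment test therefore falls inside a window on almost any day. Whether it is used is not stated. The ECG bullets say scheduled, which points to exclusion. The windows point to inclusion: the allowance for Visit 16 itself is 7 days either side (SAP Table 1), against a window of 336 days. For laboratory data nothing points to exclusion.

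If unscheduled records are eligible, a window can hold several. SAP 11.3.3 has one rule for reducing records to a single value. It averages three measurements and refers to the baseline visits. Nothing says whether to take the nearest, the last, the worst or the mean of several records in an OLE window. Choosing the record nearest the target day, or averaging, could remove an abnormal ECG that lies inside the window.

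**2. From by-visit counts to subjects ever abnormal**

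Let *p* be the proportion abnormal in each row for one category, and *k* the number of rows. The documents give no *p*, so the values below are assumptions. Every subject is taken to be observed in every row.

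- Minimum ever abnormal (the same subjects each time): *p*
- Independence between rows: 1 − (1 − *p*)^*k*
- Maximum (different subjects each time): min(1, *kp*)

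| *k* | *p* | Minimum | Independence | Maximum |
|---|---|---|---|---|
| 9 (ECG) | 1% | 1% | 8.6% | 9% |
| 9 (ECG) | 2% | 2% | 16.6% | 18% |
| 9 (ECG) | 5% | 5% | 37.0% | 45% |
| 17 (laboratory) | 1% | 1% | 15.7% | 17% |
| 17 (laboratory) | 2% | 2% | 29.1% | 34% |
| 17 (laboratory) | 5% | 5% | 58.2% | 85% |

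At 2%: 1 − 0.98^9 = 0.166 and 9 × 0.02 = 0.18; 1 − 0.98^17 = 0.291 and 17 × 0.02 = 0.34.

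Per 100 subjects, nine ECG rows each showing 2 subjects are compatible with any number from 2 to 18 ever abnormal.

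**The case against.** A reader might infer from the word scheduled that tests done for symptoms are left out of the tables and count as zero. The documents do not support that. SAP 11.3.2 never uses the word, and the laboratory windows would hold almost any on-treatment blood test. For ECGs, the same section that says scheduled also applies windows without gaps, so the text is ambiguous rather than exclusionary. Only results after the last dose clearly fall outside the windows.

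Four further points can be made for the plan.

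- **Adverse event tables.** Protocol 10.1.1 and 10.2 turn many abnormal results into adverse events, and SAP 11.3.1 counts each subject once per preferred term over the OLE. That is an ever-count, and symptom-driven tests are the likeliest to feed it. However, it counts reported terms and not crossings of the QTcF, heart-rate or laboratory limits that the SAP has chosen.
- **Listings and by-visit extremes.** Listings hold every value, and the by-visit minimum and maximum show whether any tabulated value is extreme. Where every row for a limit is zero, the ever-count for the tabulated records is zero too. Otherwise neither source gives a number of subjects.
- **Table shells.** They are in a separate document (SAP Section 4) and could contain such a row. The SAP lists its ECG tables and does not call for one.
- **Descriptive purpose.** No test or primary conclusion depends on these tables, no data are lost, and SAP Section 4 allows supplementary analyses in the study report. This stands, and it limits the weight of the point.

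The percentages are also illustrative. Dropout will reduce the number of rows per subject, and values within a subject are unlikely to be independent.

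**Conclusion.** The point holds in two parts. First, SAP 11.3.2 and 11.3.3 plan no ECG or laboratory table giving the number of subjects with at least one threshold crossing during the OLE, and by-visit counts cannot recover it. At an assumed 2% per row with complete observation, the compatible range is 2% to 18% over nine ECG rows and 2% to 34% over 17 laboratory windows. The 16.6% and 29.1% under independence are points within those ranges, not upper bounds.

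Second, the SAP does not settle how unscheduled or multiple records in a window are handled. For ECGs, the wording and the windows pull in different directions, so an abnormal symptom-driven record may be lost or diluted. For laboratory data, the gap is only the missing selection rule. That such tests are in fact excluded is not established for either.

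This is an inexpensive improvement to a descriptive safety report. It does not invalidate the planned tables.

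**What to change.** Add to SAP 11.3.2 and 11.3.3 an any-time-during-OLE summary by OLE treatment group, with each subject counted once per category:

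- highest and lowest QTcF against the limits already listed, and the largest QTcF change in each direction;
- highest heart rate and largest heart-rate increase;
- worst shift from baseline for each laboratory parameter.

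State that these rows use all on-treatment results, scheduled and unscheduled. Keep the by-visit tables, and state for them whether unscheduled records are eligible and which record represents a window that holds more than one. Close the laboratory gap at days 2757 to 2759 in the same revision.

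The cost is a few extra programmed rows and two or three sentences in the SAP. The data are already collected, and no new tests are needed.
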